### 1.2 Specific Aims

- 1) To refine a caregiver-directed intervention and study protocol based on acceptability feedback from an open pilot study with exit interviews.

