### *9.7 Instrument Administration*

A member of study staff trained in qualitative interviewing will facilitate the interviews over the phone or in person using a semi-structured interview guide with open-ended questions and response probes ([Appendix 31.09](#)), and the interview will last approximately 30 minutes. All interviews will be audio-recorded; study staff will ask for permission to turn on the audio-recorder prior to beginning each interview. A script for administration of the qualitative interview over the phone is included as [Appendix 31.14](#).

The brief enrollment survey (Appendices [31.03](#), [31.04](#)) and the 7-item Generalized Anxiety Disorder measure ([Appendix 31.01](#)) may be completed by participants via mail correspondence, online using a secure website (REDCap), over the phone, or in clinic at MGH, in accordance with participant preferences and availability. The message templates for administration of the GAD-7 and enrollment survey by mail and REDCap are included as Appendices [31.11](#) and [31.12](#), respectively. A script for survey administration over the phone is included as [Appendix 31.13](#). Only participants who have a GAD-7 score  $\geq 5$  will be registered in OnCore and complete the qualitative interview. Caregivers with GAD-7 scores  $< 5$  will be considered ineligible for the study. If a caregiver is ineligible based on his or her GAD-7 score but is still interested in the study, we will re-approach in 3 months and re-administer the GAD-7.

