## 11.2 Analysis Plan

Feasibility will be defined by rates of enrollment and participation. We will report the proportion of eligible caregivers who agree to participate in the intervention and the proportion of intervention visits completed by each participant. Additionally, we will examine reasons for declining participation, incomplete session attendance, and early withdrawal from the study. The intervention will be deemed feasible if at least 70% (+/- 18%) of eligible caregivers are enrolled in the study and if at least 70% of enrolled participants complete  $\geq 50\%$  of the sessions. We will use descriptive statistics to summarize the demographic and clinical characteristics of caregivers enrolled in the study. We will audio-record and transcribe the individual semi-structured exit interviews and analyze qualitative data according to NIH Best Practices for Mixed Methods Research in the Health Sciences. Study staff will independently review the transcripts to create a thematic framework for interpretation. Two individuals, including the Principal Investigator, will independently code the data to enhance validity and credibility, until high reliability is achieved (Kappa>0.80). The planned sample size will allow us to collect comprehensive feedback and ensures sufficient number of participants to achieve thematic saturation. In an exploratory analysis, we will also examine changes in caregiver-reported outcomes from baseline to post-intervention using paired t-tests.

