## **13.0 Withdrawal of Subjects**

We do not anticipate that any research participants will be withdrawn from the study without their consent. If a participant requests withdrawal from the study, we will ask them if they are comfortable sharing the reason for withdrawal to ensure that there are no adverse events to report to the IRB. We will ask the study participant if they are still willing to permit the study team to continue to monitor their health record, but withdraw from all other study procedures.

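### Caregivers who withdraw before the post-intervention assessment are not asked for the questionnaires or exit interview that the plan uses

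*Combined protocol and SAP*

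**What the plan says.** Section 13.0 puts two questions to a caregiver who asks to withdraw. The first is whether they are willing to give a reason. This is voluntary, and its stated purpose is safety reporting: "sharing the reason for withdrawal to ensure that there are no adverse events to report to the IRB". The second is whether the team may "continue to monitor their health record, but withdraw from all other study procedures". No other option is described.

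The data table in Section 11.3 lists the HADS, CarGOQoL, CRA, CASE and MOCS before and after the intervention, and the exit interview after it. It has no row for health-record data during follow-up.

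The analyses rest on those items. Section 1.2 has one numbered aim, to refine the intervention and protocol "based on acceptability feedback from an open pilot study with exit interviews". On the questionnaires, Section 11.2 states that "we will also examine changes in caregiver-reported outcomes from baseline to post-intervention using paired t-tests". On the interviews it states: "The planned sample size will allow us to collect comprehensive feedback and ensures sufficient number of participants to achieve thematic saturation". It also plans to examine reasons for "incomplete session attendance, and early withdrawal from the study". Its attendance criterion is that "at least 70% of enrolled participants complete" at least half of the sessions.

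**The concern.** The arrangement offered to a leaver does not match what the study needs. It keeps open a data source with no stated use after withdrawal, and closes the sources for Aim 1 and the exploratory analysis. Section 13.0 does not name the questionnaires or the interview, but the Section 11.3 table makes them study procedures, so they end with the rest.

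Caregivers who leave before the post-intervention assessment may judge the acceptability of the intervention differently from those who stay, and Aim 1 is about acceptability. If they are not asked, the feedback used to refine the intervention comes only from those who did not leave, plus whatever short reasons the leavers volunteer. The paired changes are restricted in the same way. Section 11.2 has no rule for missing post-intervention values and does not say to whom a mean change applies, although Section 11.1 expects the data to inform the effect size for a later randomized trial.

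**Working it through.** **The plan's own figure.** The only reproducible statistical figure nearby is the 18% margin on the 70% enrollment criterion in Section 11.2. With n = 25 and a two-sided 95% level (the level is not stated), 1.96 × √(0.7 × 0.3 / 25) = 0.1796, which rounds to 18%. Nothing below depends on it. For the paired tests the documents give no SD, effect size, power or dropout rate, so there is no calculation to reproduce.

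**What continues and what is used.** This applies to a withdrawal request made before the post-intervention assessment.

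| Item | Use in the plan | After the request |
|---|---|---|
| Health-record monitoring | No follow-up row in 11.3, no use in 11.2 | Continues if permitted |
| Reason for leaving | Examined in 11.2 | Asked, optional |
| Post-intervention HADS, CarGOQoL, CRA, CASE, MOCS | Paired t-tests in 11.2 | Ends |
| Exit interview | Aim 1, thematic analysis in 11.2 | Ends |

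**Would the feasibility rule show the loss?** Not necessarily. A caregiver who completes 3 of 6 sessions has completed 50% and meets the attendance threshold. If that caregiver then withdraws, the criterion is still met for them, but there is no exit interview.

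**Illustrative range.** No withdrawal rate is given, so k = 2 to 7 withdrawals of 25 is assumed. The upper value is borrowed from the attendance criterion: 18/25 = 72% meets 70% and 17/25 = 68% does not, so at most 7 can fall short of half the sessions with the criterion met. That is not a withdrawal count, and it is neither a forecast nor a cap.

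- Interviews and pairs left = 25 − k: 23 for k = 2, 18 for k = 7. This assumes that everyone else supplies both.
- 95% CI half-width for a mean change, in SDs of the change = t(0.975, n − 1) / √n:
  - n = 25: 0.413
  - n = 23: 0.432
  - n = 18: 0.497
- Shift in the mean change from leaving these caregivers out = (k / 25) × δ, where δ is the difference in mean change, in SDs, between those who stay and those who leave. The documents give neither the size nor the sign of δ. If δ were 0.5 SD in either direction, the shift would be 2/25 × 0.5 = 0.04 SD to 7/25 × 0.5 = 0.14 SD in that direction. If δ = 0 there is no shift.

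The loss of precision is modest. The main cost is views not heard.

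**The case against.** The strongest reply is that ending study procedures is what withdrawal ordinarily means, so Section 13.0 contains no error or contradiction. That stands: the point is an improvement to the design. It is also fair to say that much is already covered. Section 11.2 examines reasons for withdrawal, and the attendance criterion counts all enrolled participants. Section 14.0 lets a distressed participant stop the intervention without calling that withdrawal, Section 11.3 sets no attendance condition on post-intervention data, and question 3 of the exit interview (Appendix 31.09) asks what prevented attendance. The proposed request is optional, just as the reason is. What remains is that a reason, asked for to detect adverse events, is a poor substitute for an interview of 21 questions on timing, length, format and content.

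Several stronger readings are tempting but not supported:

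- *All withdrawers are lost.* Nothing in Section 13.0 removes data already collected. A caregiver who withdraws after completing the post-intervention questionnaires still has a pair.
- *The plan promises an interview from everyone.* Section 9.7 says that only those with a GAD-7 score of at least 5 "will be registered in OnCore and complete the qualitative interview". That restricts eligibility; it does not guarantee completion.
- *Saturation fails if anyone leaves.* Section 11.2 calls the planned sample sufficient. It states no minimum and does not say that all 25 are needed.
- *The share of all 25 who found the intervention helpful becomes uncertain by k/25.* The arithmetic would be right, but Section 11.2 plans thematic coding and no such proportion.

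**Conclusion.** The point holds for caregivers who request withdrawal before the post-intervention assessment. For them, the exit-interview feedback and the exploratory paired changes will be missing, apart from any reason they offer. Caregivers who miss or stop sessions but stay in the study are not affected, and neither is the primary feasibility endpoint.

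The size and direction of any bias cannot be stated, and with no such withdrawals there is no effect. Under the assumed 2 to 7 withdrawals, 23 to 18 interviews and pairs remain and the CI half-width rises from 0.41 SD to between 0.43 and 0.50 SD. This is a cheap improvement of low severity and does not threaten the main result. The conclusion rests on reading the questionnaires and interview as part of the procedures that end. The consent pages were not available and may say more about withdrawal.

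**What to change.** In Section 13.0, add: 'A caregiver who asks to withdraw before the post-intervention assessment will be asked once, voluntarily, whether they will still complete the post-intervention questionnaires and/or a brief exit interview by mail, REDCap or phone. Those who decline will not be asked again for study data; the distress support in Section 14.0 is unaffected.' Caregivers who stop sessions but do not withdraw should remain due for all post-intervention assessments, as now.

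In Section 11.2, add that the report will give the numbers enrolled, withdrawn and paired. It should say that mean changes, with 95% CI, apply to those with post-intervention data, and give the number of exit interviews that came from caregivers who withdrew. The paired t-test can stay, and no imputation is needed.

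The cost is two sentences in Section 13.0, a short reporting statement in Section 11.2, and possibly matching consent wording. The request fits into the conversation that Section 13.0 already plans. Section 9.7 already allows phone for the exit interview, and mail, REDCap and phone for the GAD-7 and enrollment survey; the amendment would extend those routes to the post-intervention battery. The downside is a small contact effort and a modest burden on people who have chosen to leave, which is why the request is made once and a partial response is accepted. It recovers information only as far as people agree.

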## **14.0 Risks to Subjects**

We do not anticipate that participants in the psychological intervention or qualitative interviews will experience any serious adverse reactions. If a participant expresses distress during the psychological intervention visits or exit interviews, they will be reassured by the psychologist and the research staff that

they can stop the intervention and they need not answer any of the interview questions which they find upsetting. They will also be reminded that study participation is voluntary. If participants remain distressed, both the Principal Investigator and the oncologist will be notified. Additionally, we will offer participants who remain distressed an opportunity to meet with either the principal investigator ([name]) or a clinical psychologist ([name], a co-investigator) to help address their distress. Should participants require further support, we will offer them an opportunity to meet with the MGH Neuro Oncology Clinic social worker for additional follow-up.

## **15.0 Potential Benefits to Subjects**

Preliminary data have demonstrated that more than 50% of caregivers of patients with malignant gliomas have clinically significant anxiety at the time of their loved one's diagnosis, with almost two-thirds endorsing anxiety over their course of illness. The proposed psychological intervention aims to decrease anxiety and promote coping in this highly burdened caregiver population. Participation in this study may help to improve caregivers' mental health by addressing their unique supportive care and coping needs.

## **16.0 Vulnerable Populations**

We plan to include pregnant women in this study. As this is a psychological and behavioral study only, additional safeguards are not needed for this population. No other vulnerable populations will be included in this study.

## **17.0 Community-Based Participatory Research**

N/A

## **18.0 Sharing of Results with Subjects**

We will provide the research team contact information to each participant and encourage them to contact us if they would like to receive updates and information on the research findings.

## **19.0 Setting**

Study staff will review the outpatient clinic schedule for the Yawkey 9E Brain Tumor Clinic to identify patients with malignant gliomas. Staff will approach the caregivers of these patients in clinic to obtain consent and administer surveys and questionnaires. Intervention sessions will be administered in person here at MGH. Qualitative exit interviews may be administered in person at MGH or over the phone.

## **20.0 Resources Available**

### *20.1 Team Qualification and Oversight*

The overall PI of the project ([name]) is responsible for full oversight of the project. [name] currently has 60% of her time protected to conduct research activities. She will be meeting with study staff on weekly basis (and more often as urgent issues arise) to ensure the study process is being followed accurately and to address potential challenges or issues as they may arise. [name] is a member of the MGH Cancer Outcomes Research Program (CORE). CORE has extensive experience conducting supportive care intervention studies in oncology and has the necessary expertise to ensure the success of the proposed project. Research coordinators, all of whom previously have received CITI and consent training, will be provided study-specific recruitment training.

## *20.2 Other Resources*

There are approximately 100 new malignant glioma patients in the Yawkey 9E Brain Tumor Clinic each year, so we will need to recruit about 33% of these patients' caregivers in order to reach our target accrual of 25 caregivers over the course of 18 months.

See Section 14.0 for a description of the resources available to subjects given possible consequences of the research.

## **21.0 Prior Approvals**

We will obtain IRB approval prior to initiating any study procedures.

## **22.0 Recruitment Methods**

Study staff will review the outpatient clinic schedule for the Yawkey 9E Brain Tumor Clinic to identify patients with malignant gliomas. To facilitate identification of potential participants and assess eligibility, study staff will review minimum necessary medical record data via a HIPAA waiver. This will ensure that caregivers are potentially eligible to participate in the study prior to contacting them to obtain informed consent. Prior to contacting potential participants identified via screening, the patient's primary treating oncologist will be contacted by email to inform them that we plan to approach the patient's caregiver for study participation and to inquire about any concerns regarding study participation. The email template for obtaining permission from oncologists is included as [Appendix 31.10](#). If clinicians have specific concerns about the appropriateness of enrolling a particular caregiver, we will not contact that caregiver.

A member of study staff (e.g. PI, Research Assistants) will obtain informed consent in-person prior to initiating any study measures. Research assistants, all of whom previously have received CITI and consent training, will be provided study-specific recruitment training. Caregivers who would like more time to consider participation at in-clinic approach are able to take the consent forms home with them to review. Caregivers will be provided with study staff contact information if any questions or concerns regarding the research arise.

Study staff will register eligible participants in the Clinical Trials Management System (CTMS) OnCore as required by DF/HCC SOP REGIST-101 after the participant completes the brief enrollment survey. Caregivers who report GAD-7 scores <5 will be considered ineligible for the study and will not be registered in OnCore. Caregivers who do not complete the brief enrollment survey will not be registered in OnCore.

## **23.0 Local Number of Subjects**

A total of 25 subjects (excluding screen failures) will be accrued locally. We expect more than 50% to demonstrate at least mild anxiety (GAD-7 score of 5 or greater) so total accrual of no more than 50 caregivers including screen failures should be necessary.

## **24.0 Provisions to Protect the Privacy Interests of Subjects**

To safeguard participant information and confidentiality, all data will be stored in locked cabinets in study staff's offices, in password-protected computer files, and in REDCap databases, all of which are accessible only to trained and IRB-approved study staff. Participants' data will be identified by an ID

number only, and a link between names and ID numbers will be kept separately under lock and key or in a separate password protected document accessible only by study staff.

## **25.0 Compensation for Research-Related Injury**

We do not anticipate any research-related injury due to involvement in this supportive care intervention.

## **26.0 Economic Burden to Subjects**

There will be no financial burden on study participants.

## **27.0 Consent Process**

As stated previously, a member of study staff (e.g. PI, Research Assistant) will obtain informed consent in-person during clinic appointments or infusion prior to initiating any study measures. Research assistants, all of whom previously have received CITI and consent training, will be provided study-specific recruitment training. Caregivers who would like more time to consider participation at in-clinic approach are able to take the consent forms home with them to review. Caregivers will be provided with study staff contact information if any questions or concerns regarding the research arise.

We will follow all the requirements of SOP: Informed Consent Process (CON-100) in obtaining informed consent for study participants.

## **28.0 Process to Document Consent in Writing**

As stated previously, all caregivers participating in the study will provide written informed consent.

## **29.0 Drugs or Devices**

N/A

## 31.0 Appendix

### 31.01 7-Item Generalized Anxiety Disorder (GAD-7)

#### GAD-7

Over the last 2 weeks, how often have you been bothered by any of the following problems?

	Not at all	Several days	More than half the days	Nearly every Day
1 Feeling nervous, anxious or on edge	0	1	2	3
2 NOT being able to stop or control worrying	0	1	2	3
3 Worrying too much about different things	0	1	2	3
4 Trouble relaxing	0	1	2	3
5 Being so restless that it is hard to sit still	0	1	2	3
6 Becoming easily annoyed or irritable	0	1	2	3
7 Feeling afraid as if something awful might happen	0	1	2	3

## 31.02 Hospital Anxiety and Depression Scale (HADS)

**INSTRUCTIONS:** Read each item and please select the answer which comes closest to how you have been feeling, on the average, IN THE PAST WEEK:

1. I feel tense or "wound up."
  - a. Most of the time
  - b. A lot of the time
  - c. From time to time, occasionally
  - d. Not at all
2. I still enjoy the things I used to enjoy.
  - a. Definitely as much
  - b. Not quite as much
  - c. Only a little
  - d. Hardly at all
3. I get a sort of frightened feeling as if something awful is about to happen.
  - a. Very definitely and quite badly
  - b. Yes, but not too badly
  - c. A little, but it doesn't worry me
  - d. Not at all
4. I can laugh and see the funny side of things.
  - a. As much as I always could
  - b. Not quite so much now
  - c. Definitely not so much now
  - d. Not at all
5. Worrying thoughts go through my mind.
  - a. A great deal of the time
  - b. A lot of the time
  - c. From time to time but not too often
  - d. Only occasionally
6. I feel cheerful.
  - a. Not at all
  - b. Not often
  - c. Sometimes
  - d. Most of the time
7. I can sit at ease and feel relaxed.
  - a. Definitely
  - b. Usually
  - c. Not often
  - d. Not at all
8. I feel as if I am slowed down.
  - a. Nearly all the time
  - b. Very often
  - c. Sometimes
  - d. Not at all

9. I get a sort of frightened feeling like "butterflies" in the stomach.

- a. Not at all
- b. Occasionally
- c. Quite often
- d. Very often

11. I feel restless as if I have to be on the move.

- a. Very much indeed
- b. Quite a lot
- c. Not very much
- d. Not at all

13. I get sudden feelings of panic.

- a. Very often indeed
- b. Quite often
- c. Not very often
- d. Not at all

10. I have lost interest in my appearance.

- a. Definitely
- b. I don't take so much care as I should
- c. I may not take quite as much care
- d. I take just as much care as ever

12. I look forward with enjoyment to things.

- a. As much as I ever did
- b. Rather less than I used to
- c. Definitely less than I used to
- d. Hardly at all

14. I can enjoy a good book or radio or TV

program.

- a. Often
- b. Sometimes
- c. Not often
- d. Very seldom

### 31.03 Brief Demographic Survey

#### 1. Gender

- Man
- Woman
- Specify: \_\_\_\_\_

#### 2. Relationship to patient

- Married or living as if married
- Non-cohabiting relationship
- Divorced/Separated
- Child (daughter or son)
- Parent (mother or father)
- Sibling (brother or sister)
- Friend
- Other (please specify) \_\_\_\_\_

#### 3. Race

- American Indian or Alaskan native
- Asian
- African American or Black
- Hispanic
- Native Hawaiian or other Pacific Islander
- White
- Other (please specify) \_\_\_\_\_

